Rapid reduction of sNVP with mirtazapine treatment has been reported in case series of pregnant persons^{17,18} who have not responded to other medications. These cases include mothers who requested terminations of desired pregnancies due to inability to tolerate sNVP. Reproductive outcomes for mirtazapine do not indicate an elevated risk for birth defects, although the number studied is relatively small (≈500). Medications commonly used to treat sNVP are first-line drugs; however, a substantial number of pregnant persons do not respond adequately and novel therapeutics are urgently needed.

Mirtazapine is a compelling candidate to expand therapeutic options for sNVP. This exploratory/developmental phase 2 project is designed to determine whether a Phase 3 randomized controlled trial (RCT) is warranted by establishing the acceptability, tolerability, dosing and safety of mirtazapine for sNVP. Mirtazapine is not approved by the FDA for treatment of nausea and vomiting of pregnancy (NVP); therefore, in this clinical trial, mirtazapine is an investigational product.

We will conduct a 3-week open trial of 25 pregnant persons who have not responded to at least two antiemetic drugs. We hypothesize that mirtazapine will exhibit satisfactory acceptability, tolerability and safety in pregnant persons with sNVP. After the initial trial, a continuation period or a mirtazapine tapering regimen with monitoring will be offered. The aims of the trial are:

1. Determine the acceptability of mirtazapine for sNVP that does not respond to two standard drugs.

2. Define the tolerability and safety of an escalating 3-week mirtazapine dose regimen.

3. Assess the duration of treatment required following the initial 3-week trial and the adequacy of a tapering regimen for persons who discontinue mirtazapine.

4. Determine pregnancy and neonatal outcomes for all enrolled persons. We will collect data on delivery outcomes only with the peripartum events scale

5. Explore the relationship of study drug dose and plasma concentration with side effects and pharmacogenetics by obtaining weekly plasma.

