Med Log \rightarrow	\rightarrow	\rightarrow	\rightarrow	\rightarrow	\rightarrow	\rightarrow	\rightarrow	\rightarrow	\rightarrow	\rightarrow	\rightarrow	\rightarrow	\rightarrow	\rightarrow	\rightarrow	\rightarrow	\rightarrow	\rightarrow	\rightarrow	\rightarrow		

Trial Protocol Overview (Figure 3).

Acceptability. The participant's medical status and drug treatment for sNVP will be reviewed by the study obstetrician. As in clinical practice, other anti-emetic drugs may be continued if desired by the participant and recommended by the obstetrician. The subject's decision to accept or decline will be recorded and she will be asked to provide the reason(s) for her decision. Pregnant persons who enroll will be given mirtazapine to begin treatment that evening or at a time recommended by the obstetrician. Intervention for pregnant persons who decline to participate will be coordinated by their obstetrical care professional.

Mirtazapine Regimen. The dose of mirtazapine for depression (15-45 mg/day) may not be the same as for achieving its antiemetic effect because the targeted receptors differ. We will begin with 15 mg, which is the lowest dose of the oral disintegrating tablet available. A telephone or telehealth follow-up for side effects will be conducted on day 2. Dose increases will occur weekly during the visits as depicted in Figure 3 unless the patient has prohibitive side effects or remission of sNVP. Remission is defined as a PUQE score of 3 (no symptoms) or 4 (1 hour or less of nausea without retching or vomiting). Side effects assessment will occur the day after each dose increase to evaluate tolerability. Reduction to the previous dose will occur if side effects are burdensome. Although the modal dose of mirtazapine from case reports is 30 mg. tolerability studies in persons with NVP have not been published. Steady-state plasma concentrations of mirtazapine occur within 5 days³² and will be achieved across the week prior to dose escalations. Weekly plasma concentrations will be obtained to confirm absorption of mirtazapine and explore associations with side effects. Sampling will occur at a consistent time of day for each woman; ideally, the time will be in the late afternoon during the drug elimination phase as close to the trough concentration as feasible. Adverse events will be reviewed by the DSMB after every 5 subjects to determine whether a protocol or dosing change is warranted.

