Both compliance with treatment and vomiting within an hour of the dose will be recorded in REDCap (along with the daily PUQE score) to evaluate these factors in the interpretation of

plasma concentrations. Mirtazapine treatment will continue unless the participant withdraws consent, experiences a limiting side effect or an obstetrician decides that the health risk to the patient compels discontinuation. At the end of the 3-week trial, subjects will be asked whether they prefer to continue mirtazapine, which will also serve as a measure of treatment satisfaction. Pregnant persons who choose to stop treatment will be given a taper regimen in reverse order of the dose escalation required for the 3-week trial. For example, if a patient is taking 45 mg at the end of week 3, she will begin a taper (by week) of 30 to 15 to 7.5 to 0 mg. If she relapses or has discontinuation symptoms, the previous effective dose will be given. She may attempt to taper again with the same approach. Participants who continue to be treated with mirtazapine in the continuation phase will be followed monthly throughout pregnancy unless they withdraw consent.

Maintenance Drug Treatment (Figure 4). For pregnant persons who choose to continue treatment, mirtazapine will be prescribed at the dose achieved at the end of the 3-week trial. The duration of treatment will be decided by the patient with a study obstetrician based upon her response and comfort with drug discontinuation. These data will be novel since no information on the duration of treatment with mirtazapine in persons with sNVP is available. For persons treated until delivery, maternal and cord blood will be obtained for plasma mirtazapine concentration measurement to evaluate placental transfer. If postpartum mirtazapine treatment is desired, it will be coordinated with our Collaborative Care Perinatal Services (COMPASS - the integrated mental health program in the Obstetrics department), or in the Asher Center in the Department of Psychiatry, which [name] directs.

Figure 4: Data Collection: Continuation Treatment					
Maintenance (every 4 weeks)	Delivery				
Wt, Ht, BP PUQE GH Plasma PHQ-9 GAD-7 C-SSRS ASE SS Medication Log	PES Maternal and umbilical cord blood				
Log PUQE=Pregnancy Unique Quality of Emesis; PHQ-9=Patient Health Questionnaire; GAD-7 =Generalized Anxiety Disorder; C-SSRS=Columbia-Suicide Severity Rating Scale; ASE=Asberg Side Effects; SS=Screen for Serotonin Syndrome. PES, Peripartum Events Scale.					

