The DSMB will review specifically the frequency of adverse study-associated events in all subjects as follows: 1) acceptability data; 2) the tolerability of the mirtazapine dosage regimen; 3) mirtazapine discontinuation and reason(s) for discontinuation; 4) emergency room visits; 5) post-enrollment hospitalizations, durations and interventions; 6) additional medication exposures during the three week and optional maintenance study periods; 7) the adequacy of the tapering regimen to mitigate discontinuation symptoms, the number of pregnant persons who experience recurrence of sNVP and the number tapers that are attempted; 8) patient complaints to the study team or IRB; and, 9) reproductive outcomes for both the mother and the neonate on the Peripartum Events Scale, which will be compared to the outcomes of data from in-utero SSRI antidepressants. These findings will be evaluated and summarized by neonatology consultant [name].

The DSMB meetings will occur by teleconference. The data will be summarized and provided prior to the phone consultations to the DSMB members. The tables below summarize the activities of the DSMB.

YEAR 01	YEAR 02
Prior to initial meeting: discuss and sign agreement and expectations for DSMB participation; develop format for minutes at all meetings.	Continue quarterly teleconferences; adjust data delivery format as appropriate per DSMB input.

Initial meeting: Review protocol, establish the data to be reviewed by the DSMB; set additional quarterly phone conferences with option for as needed meetings. A particular focus will be assessment of the tolerability of the dosing strategy and the potential need for modification.	Final meeting: review course of study; summarize untoward events, quarterly phone; review and generate final report.
Quarterly: Review course of study to date, summarize any untoward events, problem solve. Data summaries provided to DSMB members at least 10 days prior to quarterly conference reviews.	

PROVISIONS TO PROTECT THE PRIVACY INTERESTS OF PARTICIPANTS

Subjects will be informed regarding staff who will have access to their data. Topics covered in questionnaires are consistent with standard of care evaluations and are not expected to induce any additional discomfort or distress.

Authorized research personnel may have access to enrolled subjects' medical records at the designation of the Principal Investigator in compliance with EDW policy.

COMPENSATION FOR RESEARCH-RELATED INJURY

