Endeavor to Stop Nausea/Vomiting Associated with Pregnancy (E-SNAP) NCT05452174 09/30/2020

STATISTICAL DESIGN AND POWER ANALYSIS

Our data management team includes a highly experienced clinical trials statistician and database programmer. The REDCap management system was developed and functioning at Northwestern and is being transferred via a DUA. We are mindful of subjects' time and we send links to allow women to enter self-report measure data from home (for example, for recording of daily PUQE scores).

Analytic Approach. Descriptive statistics such as demographic and baseline clinical information will be summarized for all eligible women. These results will inform the feasibility, design and statistical approach for construction of the subsequent randomized controlled trial if the findings from the proposed study demonstrate the acceptability and feasibility of the protocol. This R21 study is not expected nor intended to have the power to address the outcomes described below, but to provide data to guide the design of a phase 3 RCT.

Aim 1. Define acceptability of mirtazapine for refractory NVP. Acceptability is defined by the number of women who accept participation compared to the total who undergo the consent procedure. All women will be asked for the reason behind their decision. A standard consort chart¹ will be created to record subject flow through the protocol. The acceptability of mirtazapine for NVP/HEG is a factor in the feasibility of the eventual RCT and is an important factor in the ability to recruit subjects and define the number of sites required.

Aim 2. Determine the tolerability and safety of the dosing regimen. Measures of tolerability include the proportions of: 1) emergent side effects on the ASE, which will be isolated by comparison to symptom ratings at intake; 2) withdrawals attributable to side effects; and 3) women who elect to continue mirtazapine after the initial 3-week trial. The daily PUQE scores will be used to evaluate the time (in days) to remission during the 3 week trial. We will use Kaplan-Meier curves to visualize time to remission (defined by a PUQE score of 3 or 4. Additionally, we will fit Cox regression models to identify factors that may be associated with time to remission.

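### Aim 2 counts choosing to continue mirtazapine as tolerability but does not count doses reduced or increases withheld because of side effects

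*SAP*

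**What the plan says.** The second aim in the protocol (Objectives) is to "Define the tolerability and safety of an escalating 3-week mirtazapine dose regimen". The SAP, under Aim 2, says that the measures of tolerability include three proportions:

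1. "emergent side effects on the ASE, which will be isolated by comparison to symptom ratings at intake";
2. "withdrawals attributable to side effects";
3. "women who elect to continue mirtazapine after the initial 3-week trial".

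Under Mirtazapine Regimen the protocol schedules weekly dose increases "unless the patient has prohibitive side effects or remission of sNVP", and adds: "Reduction to the previous dose will occur if side effects are burdensome". The same section says that women will be asked at the end of week 3 whether they want to go on with the drug, "which will also serve as a measure of treatment satisfaction". Under Maintenance Drug Treatment, those who go on do so at the dose they had reached, and the length of further treatment depends on response and on how comfortable the woman is about stopping.

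The section on monitoring participant safety has the DSMB review both the tolerability of the dose regimen and "mirtazapine discontinuation and reason(s) for discontinuation". Neither document lists dose reductions or withheld increases as an outcome.

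**The concern.** The continuation choice mixes several things. A woman who is well and sees no need for more drug lowers the proportion without having been intolerant. A woman with troublesome effects but good relief may raise it. A low or high figure therefore cannot be read as tolerability without knowing the reasons.

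The regimen also has its own response to intolerance: hold the dose or step back. Both are informative about whether the escalation could be tolerated, and neither is counted. Stepping a woman down also makes it less likely that she withdraws, so the event that the SAP does count becomes rarer as the event that it does not count becomes commoner.

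This matters for the next trial. The SAP intends to weigh speed of response against side effects when deciding whether the dosing for the randomised trial should change, including towards a more forceful schedule. How many women reached and held each step is a main input to that decision.

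**Working it through.** **The plan's own figure.** The only sample-size figure that bears on these proportions is enrolment: 20 evaluable women and 20% dropout give 20 / (1 − 0.20) = 25, which agrees with the SAP. No expected tolerability rate, threshold or precision is stated, so there is no tolerability figure to reproduce.

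**Following one woman through the three measures.** Suppose that a dose increase brings burdensome side effects, she is returned to the previous dose, and at week 3 she chooses to continue.

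- Withdrawals for side effects: not counted, because she did not withdraw.
- Election to continue: counted, at the lower dose.
- Emergent ASE symptoms: probably counted, since side effects are assessed the day after each increase and at each weekly visit. The SAP gives no severity cut-off and no link to a dose change, so she falls in the same proportion as a woman with a mild new symptom and no change of dose.

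The final dose does not recover the information either. Increases are withheld for remission as well as for side effects, so a woman still on the first step at week 3 may be there for opposite reasons.

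**Illustration, all counts assumed.** Take 20 evaluable women, 2 of whom stop because of side effects. Let a be the number who tolerated the regimen but choose to stop because their symptoms resolved, and b the number stepped down for side effects who continue; no woman is in both groups.

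- Continuation = (20 − 2 − a) / 20
- Tolerated escalation (no stop and no step-down for side effects) = (20 − 2 − b) / 20
- Withdrawals for side effects = 2 / 20 = 10% in every row

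| a | b | Continuation | Tolerated escalation | Women on whom the two differ |
|---|---|---|---|---|
| 0 | 0 | 18/20 = 90% | 18/20 = 90% | 0 |
| 6 | 0 | 12/20 = 60% | 18/20 = 90% | 6 |
| 0 | 6 | 18/20 = 90% | 12/20 = 60% | 6 |
| 4 | 4 | 14/20 = 70% | 14/20 = 70% | 8 |

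The two departures run in opposite directions and can cancel, so even agreement between the proportions would not show that continuation is a sound stand-in. The withdrawal proportion does not tell the rows apart.

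**Precision.** Exact 95% intervals would be 68% to 99% for 18/20 and 36% to 81% for 12/20. The SAP reports that 2 women had enrolled before closure; with 2 women, an observed 0/2 gives 0% to 84%.

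**The case against.** The strongest reply is that nobody is given an overall score. The SAP reports three separate proportions, introduced as a list that need not be complete, with no composite, threshold or go/no-go rule. A reader might infer that a stepped-down woman is classified as having tolerated the regimen, or that the regimen could be declared tolerable although few women held its later steps. The documents do not support that: they contain no such classification or declaration, and the ASE results would stand beside the continuation figure. This stands, and it limits the point to the continuation item and the missing count.

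Second, tolerability by dose is partly covered elsewhere. The ASE grades severity and overall distress, the DSMB reviews regimen tolerability, and adverse events are reviewed after every 5 women. This is a real mitigation, but none of these provisions defines a count of dose actions taken for side effects.

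Third, using one choice for both satisfaction and tolerability is not a contradiction; the protocol says only that it also serves the former. That is right. The difficulty is interpretation, not inconsistency.

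Fourth, stopping at week 3 because symptoms have resolved may be uncommon. Remission halts escalation rather than treatment, and in the seven-case series cited in the protocol treatment lasted 4 to 24 weeks. That weakens this half of the point and leaves the dose-reduction half untouched.

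Finally, stepping back is part of the regimen as written, so a stepped-down woman has not failed it. True, but the aim asks about tolerability of an escalating regimen, and how often escalation had to be reversed or withheld is part of the answer.

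**Conclusion.** The point holds in this limited form. Election to continue is an indirect measure of tolerability, and Aim 2 has no direct measure of tolerated escalation, although the regimen generates the events needed for one. The separate ASE and withdrawal proportions reduce the loss but do not remove it.

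The size cannot be estimated. The gaps of 30 percentage points in either direction rest on invented counts and show only what is possible. With 2 women enrolled, the practical consequence lies in how the results are reported and in what is carried into the design of the randomised trial. The change is worth making; the point does not invalidate the other Aim 2 measures.

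**What to change.** In SAP Aim 2:

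- Add to the tolerability list the number and proportion of women with a dose reduced, an increase withheld, or drug stopped because of side effects. Give this overall, each woman counted once, and by dose step, with exact 95% confidence intervals.
- Count increases withheld because of remission separately.
- Report election to continue as treatment satisfaction, split by the reason given and by remission status at week 3.

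The cost is mainly wording. A medication log is kept and reasons for discontinuation are reviewed, but neither document says that the reason for each dose change, or for choosing to continue, is recorded. A data field for each may have to be added. The tolerability result may look less favourable, and the intervals will be wide, almost uninformative with 2 women, so the counts themselves should be shown. No treatment rule changes.

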Authorized research personnel will work with clinicians from the Northwestern Obstetrics and Gynecology services and the Obstetrical Triage program to identify potentially eligible individuals and approach them about their interest in participating. We have defined several eligibility criteria to allow participants to be screened by our study team. Subject burden can be reduced and study efficiency improved by asking only those subjects likely to be eligible to undergo a full baseline assessment. The screen includes: 1) age 2) gestational age of the fetus, 3) confirmation of plan to receive care and deliver at Prentice Women's Hospital (PWH), 4)

PUQE score of 10-15, 5) has been treated with at least two anti-emetic/antinauseant drugs with inadequate response; and 8) English speaking.

The inclusion/exclusion criteria will be reviewed in the patient's chart and documented on the screening log. If a patient meets all the inclusion criteria for enrollment, does not have any of the exclusion criteria, she will be approached about the study by authorized personnel. Her primary obstetrician will be contacted to review the patient's participation.

Brochures will be available to provide potential subjects with additional information. We will also post information about this study on our Asher Center and Northwestern Medicine websites, as well as post on the NCT site.

COMPENSATION FOR PARTICIPATION IN RESEARCH ACTIVITIES

Participants will be compensated with \$35 for each week of the three-week trial. If a participant wishes to participate in the continuation period or a mirtazapine tapering regimen, they will continue for 5 additional weeks and compensated with \$35 each week.

If a participant enters into the study early in pregnancy (gestational age of 5 weeks), they will have monthly visits after the 8 weeks is completed, for a maximum total of 10 visits.

Compensation will be provided in a form of a check at the end of each week during their followup visit.

WITHDRAWAL OF PARTICIPANTS

A participant will be withdrawn from the research without their consent if there is: 1) refusal to follow the medication protocol, and/or 2) refusal to answer study questionnaires, 3) the participant fails to respond to contact attempts from the study team.

RISKS TO PARTICIPANTS

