We will evaluate the potential need for change in the dosing for the subsequent RCT by balancing the time to response against the emergence of any side effects. For example, if the 15 mg/day dose is well tolerated but the major symptom reduction occurs at 30 mg/day, we will consider the advisability of a more assertive dosing regimen with our DSMB and FDA consultants.

Aim 3. The drug tapering strategy will be assessed by evaluating the emergence of somatic symptoms on the Asberg side effects profile during the taper. Obtaining weekly plasma concentrations in the initial 21-day trial allows an exploration of whether a relationship between mirtazapine concentration and antinauseant/ antiemetic efficacy is likely in this group of women. The patient's genotypes and corresponding phenotypes (ultrarapid, rapid, intermediate, poor metabolizers--by specific enzyme) will be evaluated for their relationship to plasma mirtazapine concentrations. Biotransformation is mediated by CYP2D6, CYP3A4, and 1A2.²

Aim 4. Evaluate the maternal and fetal safety of mirtazapine. The maternal and neonatal outcomes from the PES will be reviewed for consistently reported events across subjects. We will compare the mirtazapine exposure data to that of women who have taken SSRI through pregnancy in our Obstetric-Fetal Pharmacology U54 study (N=88), Optimizing Medication Management for Mothers with Depression. Neonatologist [name] (see letter of support) will collaborate with our team to interpret the OPTI-MOM neonatal outcome data from the PES in the proposed trial (fetal exposure to mirtazapine) and compare it with the PES from our current OPTI-MOM subjects (fetal exposure to SSRI antidepressants). We have used these measures in our studies of SSRI exposure on neonates.³ The PES includes medical and obstetric risk factors, time in the delivery/ operating room, fetal monitoring, surgical complications, infant anthropometrics, special care/NICU admission, and post-birth complications. We will compare data using t-tests, chi-square test, and nonparametric tests as appropriate according to the type of data and their distributions.

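### SAP Aim 3 judges the taper by side effects alone and omits recurrence of sNVP, and no assessment table covers the taper, which leaves tapers begun in the monthly phase thinly observed

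*SAP*

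**What the plan says.** The third aim in the Protocol (Objectives) is: "Assess the duration of treatment required following the initial 3-week trial and the adequacy of a tapering regimen for persons who discontinue mirtazapine". The SAP's answer on the taper, under Aim 3, is one sentence: "The drug tapering strategy will be assessed by evaluating the emergence of somatic symptoms on the Asberg side effects profile during the taper". The rest of SAP Aim 3 concerns plasma concentrations and genotype.

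The taper is described in the Protocol under Mirtazapine Regimen, with an example for a woman on 45 mg: "she will begin a taper (by week) of 30 to 15 to 7.5 to 0 mg". The same paragraph names two ways in which a taper can fail, relapse and discontinuation symptoms. Either one sends the woman back to the dose that had worked, and she may try to taper again. Under the provisions for monitoring safety, the DSMB is to review how well the taper limits discontinuation symptoms, and also "the number of pregnant persons who experience recurrence of sNVP and the number tapers that are attempted".

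Three places bear on what is measured after day 21:

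- Figure 3 gives the Asberg Side Effects (ASE) scale and the PUQE up to the day-21 visit and then stops.
- Figure 4 is titled for continuation treatment. Its ASE and PUQE column begins "Maintenance (every 4 weeks". The text above it agrees: "Participants who continue to be treated with mirtazapine in the continuation phase will be followed monthly throughout pregnancy".
- The compensation section says of anyone who enters the continuation period or "a mirtazapine tapering regimen, they will continue for 5 additional weeks and compensated with" a weekly payment, made at a follow-up visit. For women who enter early in pregnancy, monthly visits start once 8 weeks are complete. No assessments are listed.

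**The concern.** There are two linked gaps.

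The first is in the analysis. The ASE shows side effects and withdrawal-type symptoms. It is not the trial's measure of nausea and vomiting, which is the PUQE. A woman who comes off the drug without new somatic symptoms, but whose sNVP returns, counts as a success under the SAP and as a failed taper under the protocol. The SAP also does not say what emergence is measured against in Aim 3. Under Aim 2 the reference is intake, before any mirtazapine, and that cannot separate symptoms that arise on withdrawal from side effects already present on treatment.

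The second is in the data. An analysis of symptoms during a taper that changes weekly needs ratings at about that spacing and one just before the taper starts. No table provides them, and the places that speak to visit frequency disagree. At stake is whether Aim 3 can tell the designers of the phase 3 trial if this taper works.

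**Working it through.** The plan gives no figure for this point, so the check compares the texts and then counts visits.

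**Analysis.** Protocol criteria for a failed taper: relapse, or discontinuation symptoms. DSMB items: discontinuation symptoms, number with recurrence, number of taper attempts. SAP Aim 3: emergent ASE symptoms only. Recurrence and attempts are therefore named in the protocol and missing from the SAP. The SAP defines remission (PUQE 3 or 4, under Aim 2), but neither document gives a PUQE definition of relapse.

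**Taper begun on day 22.** Assumptions: each step lasts 7 days; tapers from 30 mg or 15 mg follow the lower part of the 45 mg example; 4-weekly visits fall on days 49, 77 and so on (21 + 28k); the weekly visits implied by the compensation section fall on days 28, 35, 42, 49 and 56 (21 + 7k, k = 1 to 5).

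| Dose at day 21 | Taper days | 4-weekly visits on taper | First 4-weekly visit after last tapered dose | Weekly visits on taper | Weekly visits after taper |
|---|---|---|---|---|---|
| 45 mg | 22–42 | 0 | 49 − 42 = 7 days | 3 | 2 |
| 30 mg | 22–35 | 0 | 49 − 35 = 14 days | 2 | 3 |
| 15 mg | 22–28 | 0 | 49 − 28 = 21 days | 1 | 4 |

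Which schedule applies thus decides between no rating on the taper and a possible rating in every taper week. In either case the day-21 ASE and PUQE give a reference just before the taper.

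**End of the weekly window.** 3 + 5 = 8 weeks, that is, day 56. A 21-day taper lies wholly inside it only if it starts by day 56 − 21 + 1 = 36.

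**Taper begun in the monthly phase.** Visits are 28 days apart and a taper of L days has L below 28, so at most one visit can fall inside it. If the start is random relative to visits, the chance that one does is L/28:

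- 3 weeks: 21/28 = 75%
- 2 weeks: 14/28 = 50%
- 1 week: 7/28 = 25%

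A taper of two or three steps therefore never has one scheduled rating per step. The latest earlier rating can be up to 28 days old. If instead the taper starts the day after a monthly visit, the reference is fresh, but the next visit is 28 days later and falls after even a 21-day taper has ended.

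**The case against.** The best case for the plan is that the compensation section implies weekly visits for 5 weeks, which covers every week of a taper begun on day 22, and that day 21 supplies the reference. Figure 4 is headed continuation treatment, so it need not govern tapers at all, and the Objectives promise a taper with monitoring. Recurrence is counted for the DSMB. The instrument section describes daily PUQE entry with no end date. Operational and analytic detail is assigned to a manual of procedures that is not public. The study is exploratory, and the SAP disclaims power for these outcomes.

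Much of this stands, and it rules out stronger readings that a reader might infer:

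- That taper adequacy cannot be assessed, or that 4-weekly visits are the only follow-up. The implied weekly visits contradict this for early tapers.
- That recurrence is ignored. It is to be reviewed by the DSMB; the gap is in the SAP.
- That most tapers fall after week 8, because the seven-case series in the Background had a mean treatment duration of 9.1 weeks. Its range was 4–24. Removing the 24-week case leaves (7 × 9.1 − 24)/6 = 39.7/6 = 6.6 weeks, so one case carries the mean past 8. The documents give no split between early and late tapers.

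What the objection does not remove: the compensation text names no assessments, disagrees with the monthly follow-up stated under Mirtazapine Regimen and in Figure 4, and ends at week 8, while late tapers and repeat attempts are allowed. The daily PUQE is drawn only to day 21 in Figure 3 and is listed among the 4-weekly measures in Figure 4. A count reviewed by the DSMB is not a planned analysis.

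**Conclusion.** The point holds in a limited form. SAP Aim 3 measures one of the two ways in which the protocol says a taper can fail, and it omits recurrence and taper attempts. No assessment table covers the taper, and the passages on visit frequency after day 21 conflict.

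For tapers begun at day 22 the effect is modest, provided that ASE and PUQE are in fact collected at the implied weekly visits. For tapers begun in the monthly phase there would be at most one scheduled rating (chance about 75%, 50% or 25% for 3, 2 or 1 weeks), and there may be none just before the start. Those percentages rest on a start that is random relative to visits, and on the 4-weekly schedule carrying on during a late taper. The second is an inference, because the documents do not say what applies then.

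This should be corrected as a cheap improvement; it is not a flaw that undermines the trial. With 25 women planned, and 2 enrolled before closure according to the SAP, only descriptive reporting is realistic. The main value now is accurate reporting and a better template for the later trial.

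**What to change.** - In the Protocol, reconcile the monthly follow-up under Mirtazapine Regimen and the 4-weekly column of Figure 4 with the weekly visits implied in the compensation section.
- Add a taper column to the assessment schedule: self-entered ASE and PUQE before the taper and at each weekly step already in the protocol, whenever the taper starts and for repeat attempts too.
- In SAP Aim 3, state that emergent symptoms are measured against the pre-taper rating.
- In SAP Aim 3, report descriptively the proportion with recurrence of sNVP and the number of taper attempts. Define recurrence on the PUQE for analysis only, and fix the definition before the data are examined.

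The cost is a schedule column, a few lines of SAP text and a few short online questionnaires per taper; online self-entry already exists. The downside is that small added burden on women who may be unwell. None of this changes a dose, a taper step or a clinical rule.
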